#### APPENDIX 1: DATA HANDLING CONVENTIONS

#### 1. IMPUTATION RULES FOR START DATES

The following imputation rules apply to incomplete start dates of adverse events and medications.

## Whole date is missing

The date of first study drug administration will be assigned to the missing fields.

## Missing day and month

- If the year is same as the year of the first study drug administration, then the day and month of the first study drug administration will be assigned to the missing fields.
- If the year is prior to the year of the first study drug administration, then December 31 will be assigned to the missing fields.
- If the year is after the year of the first study drug administration, then January 1 will be assigned to the missing fields.

## Missing month only

Treat day as missing and replace both month and day according to the above procedure.

## Missing day only

- If the month and year are same as the year and month of the first study drug administration, then the date of the first study drug administration will be assigned to the missing day.
- If the month and year are before the year and month of the first study drug administration, then the last day of the month will be assigned to the missing day.
- If the month and year are after the year and month of the first study drug administration, then the first day of the month will be assigned to the missing day.

If the stop date is complete and the imputed start date as above is after the end date, the end date will be imputed for the start date.

#### 2. IMPUTATION RULES FOR END DATES

The following imputation rules apply to incomplete end dates of medications.

#### Whole date is missing

The date of last study drug administration will be assigned to the missing fields.

## Missing day and month

If the year of the incomplete end date is the same as the year of the last study drug administration, then the day and month of the last study drug administration will be assigned to the missing fields.

- If the year of the incomplete end date is prior to the year of the last study drug administration, then
   December 31 will be assigned to the missing fields.
- If the year of the incomplete end date is after the year of the last study drug administration, then January 1 will be assigned to the missing fields.

## Missing month only

Treat day as missing and replace both month and day according to the above procedure.

## Missing day only

- If the month and year of the incomplete end date are the same as the month and year of the last study drug administration, then the day of the last study drug administration will be assigned to the missing day.
- If the month and year are before the year and month of the last study drug administration, then the
  last day of the month will be assigned to the missing day.
- If the month and year are after the year and month of the last study drug administration, then the first day of the month will be assigned to the missing day.

# 3. DERIVATION RULES OF NUMERIC VALUES OF CLINICAL LABORATORY PARAMETERS

If a character string (">x", "<x" or "=x") is reported for a parameter of the numerical type, the numeric part of the value ("x") will be derived and used in the statistical analyses. However, the actual values as reported in the database will be presented in data listings.

#### 4. MISSING DATA FOR SOM DURATION CALCULATIONS

As noted above (Section 9.1), the primary analyses will examine the duration of SOM and censor the patient's data when missing. For clarity, censored visits will carry forward the last WHO score recorded for the subject through to discontinuation. For sensitivity analyses, the data will be analyzed assuming that the SOM remains at the last recorded WHO grade for the entire trial (irrespective of early study termination) and, again, assuming that the SOM was 0 throughout the trial period.

## 5. ANALYSIS ADJUSTMENTS DUE TO IMPACT OF COVID-19 PANDEMIC

Reference is made to the FDA Guidance for Industry, "Statistical Considerations for Clinical Trials During the COVID-19 Public Health Emergency," June 2020. While many of the patients were in the treatment portion of their participation, the COVID-19 pandemic interrupted normal clinical operations with an impact on patient retention, the number and degree of protocol deviations, the ability to obtain protocol specified measurements, the ability to ship clinical specimens, and decreased the availability of clinical research personnel to perform protocol related activities. The ultimate impact of this unprecedented disruption in the clinical trial and the resulting number of dropouts, missing data, and partial data remains unclear at this time, Currently, the protocol specifies a last-value forward method of handling missing data and all patients in the mITT population are included in the analyses even if the final 4-6 weeks of experimental therapy is not delivered. To address the impact of the pandemic on this study, we will:

- Drop patients at specific sites in which the COVID-19 activities created extensive problems with documentation, data collection and/or patient enrollment and compliance;
- Terminate the trial early; and

•	Conduct sensitivity analyses on primary, secondary and safety analyses to understand the
	potential impact of the pandemic (with an assigned "start date" to the pandemic of January 1,
	2020 based on the onset of disease potentially impacting participating European sites).

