12.3. Final Analysis

Upon completion of enrollment, the study database is to be locked, released, and analyzed in two parts, the first being an analysis of data through the 6-week visit from the last RT for the last patient, and the second final analysis of all data including all long-term visit data. During these two data analyses, all site personnel will remain blinded as to individual patient dose-group assignments.

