12.5. Selection of Primary Analysis Population

Given that OM does not occur at a significant rate in patients that have not received at least 55 Gy of cumulative radiation, the primary analysis population will be limited to those patients that have received at least 55 Gy of radiation. Only those patients that receive sufficient radiation therapy are at risk of developing the disease (i.e., SOM). Should SGX942 reduce the most severe cases of OM prior to reaching 55 Gy of radiation such that there is a reduced dropout rate from anticancer therapy, the worst cases of OM in the placebo group, but not the SGX942 group, will be eliminated from the analyses. Thus, if bias is introduced, it is likely to lead to a conclusion that SGX942 is less efficacious than it actually is.

The primary efficacy analysis will be based on this mITT population that is defined as all randomized subjects receiving a minimum of 55 Gy of cumulative radiation analyzed per treatment groups defined by their randomization treatment assignment.

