#### 2 STUDY DESIGN

Approximately 260 patients will be enrolled into this Phase 3, placebo-controlled, double-blind, multinational study to evaluate the efficacy of SGX942 compared to placebo in treating the duration of SOM in patients receiving chemoradiation therapy (CRT) for the treatment of head and neck cancer (HNC). The study sample size takes into account the recommendation of the study Data Monitoring Committee (DMC) to increase the study sample size to 260 subjects. Up to an additional 10% may be enrolled to offset the impact of study dropouts (i.e., those subjects that do not receive 55 Gy radiation) and missing data which are each expected to potentially increase during the COVID-19 pandemic.

Patients will be randomized into one of two groups (1.5 mg/kg SGX942:Placebo) at a 1:1 ratio. They will be stratified by site, presence of gastrostomy tube, and human papilloma virus (HPV) status. Patients will receive their initial blinded intravenous (IV) study drug (1.5 mg/kg SGX942 or placebo) within 3 days following the initiation of RT.

The primary efficacy outcome for this study is the duration of SOM, defined as the number of days from the first oral examination with a WHO Grade assessment of 3 or 4 through the first day that a WHO Grade of <3 is recorded with no subsequent assessments ≥3 through the 6-week post-RT visit. Oral mucositis (OM) will be evaluated using the WHO score for OM.

[figure not shown]
Patients will be screened to assess their eligibility prior to randomization. After randomization, subjects will begin treatment with study drug within 3 days following the initiation of RT.

Patients will receive study drug while undergoing CRT and continue to receive study drug for 2 weeks after the completion of their RT. Dosing will be twice weekly. Study visit days will be every third day (+/-1 day). On study visit days, patients will receive the 4-minute infusion of study drug. Study drug will not be given on the same day as chemotherapy. Study drug can be given at any time during the visit day, but must occur on the same calendar day that is the study visit day. The twice weekly study drug treatment visit calendar extends to 2 weeks post-completion of RT.

Efficacy will be further assessed at the 3 through 6 weeks post-RT completion visits. Follow-up visits will be conducted at 6 and 12 months after the last radiation dose to continue to evaluate safety and secondary endpoints.

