## 3.2.3 Modified Intent-to-treat (mITT) Population

The mITT population is defined as all randomized subjects who received at least one dose of study drug and at least 55 Gy of cumulative radiation therapy. Subjects will be analyzed based on the treatment assigned.

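### The SAP's COVID-19 rule drops randomised patients at unnamed sites with no threshold, decision maker, deadline or blinding condition, against the mITT definition used for the primary analysis

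*SAP*

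**What the plan says.** Appendix 1, section 5 of the SAP lists what the sponsor will do about the pandemic. The first item is: "Drop patients at specific sites in which the COVID-19 activities created extensive problems with documentation, data collection and/or patient enrollment and compliance". Early termination of the trial is the second. The third is a separate commitment: "Conduct sensitivity analyses on primary, secondary and safety analyses", with 1 January 2020 as the assigned start of the pandemic. That date is attached to the sensitivity analyses, not to the drop rule. The paragraph introducing the list notes that, as matters stand, every mITT patient is analysed even if the last weeks of study treatment were not given.

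Protocol 10.1 places the primary endpoint analysis in the mITT, and SAP section 9 uses the mITT for efficacy unless another population is specified. SAP 3.2.3 defines that set as "all randomized subjects who received at least one dose of study drug and at least 55 Gy of cumulative radiation therapy". Protocol 12.5 has "all randomized subjects receiving a minimum of 55 Gy of cumulative radiation". Neither mentions site or COVID-19.

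For the two staged analyses, Protocol 12.3 says that "all site personnel will remain blinded as to individual patient dose-group assignments". SAP section 2 adds patients because of the pandemic: "Up to an additional 10% may be enrolled to offset the impact of study dropouts" and missing data.

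**The concern.** The bullet is written as something that will be done, under a heading about analysis, and it removes patients. It leaves open:

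- how bad a site's problems must be;
- who judges, and by what date;
- whether that person may have seen results or allocation;
- whether the whole site goes or only some of its patients;
- which analysis population is affected.

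Data collection and compliance arise after randomisation and could be influenced by treatment. A programmer cannot both analyse every patient who meets SAP 3.2.3 and drop some of them.

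At stake is the single primary test of a pivotal trial. The five hierarchical secondary endpoints use the same population. A choice informed by results could inflate the false-positive rate. A blind choice would still lose information, which works against the up to 10% extra enrolment. If whole sites go, patients who completed before 1 January 2020 are discarded as well; the protocol synopsis puts first enrolment at about November 2017.

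**Working it through.** **1. Looking for the missing elements.** The places that could supply them are these.

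| Place | What it gives | Site or COVID-19 exclusion? |
|---|---|---|
| SAP 3.2.1-3.2.4 | Safety, ITT, mITT and PP definitions | None |
| SAP 9 and 9.1 | mITT for efficacy; log-rank test | None |
| Protocol 10.1 and 12.5 | mITT for the primary analysis | None |
| Protocol 12.3 | Blinding of site personnel | Nothing on who selects sites |
| Protocol 11.6 | DMC sees unblinded data at interim analyses | No role in site exclusion |
| SAP Appendix 1, section 5 | The drop rule | No threshold, person, date or blinding |

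**2. The plan's own sample size.** Inputs from Protocol 12.4 and SAP 3.1: medians 13 and 8 days, 1:1 allocation, 90% power, alpha 0.05 (two-sided by SAP 3.3), 190 evaluable patients. With exponential durations the hazard ratio is 8/13 = 0.615 and ln(13/8) = 0.4855.

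- Schoenfeld: 4 × (1.96 + 1.2816)² / 0.4855² = 178.3 events.
- Freedman: 186 events, within 3% of 190.

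The figure of 190 is therefore a reasonable two-sided one. Calibrating to it gives 178.3/190 = 0.938 events per evaluable patient.

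**3. Power after a blind loss.** The plan gives no number to be dropped, so the lost fraction f is varied:

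Power = Φ(√(0.938 × n × (1 − f)) × 0.4855/2 − 1.96)

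Example: n = 228, f = 0.2 gives about 171.2 events and Φ(3.176 − 1.96) = 0.888.

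| Evaluable before dropping | f = 0 | 10% | 20% | 30% | Loss that brings power to 90% |
|---|---|---|---|---|---|
| 260 (planned enrolment, all evaluable) | 0.967 | 0.949 | 0.924 | 0.887 | 1 − 190/260 = 26.9% |
| 228 (assumed) | 0.944 | 0.921 | 0.888 | 0.844 | 1 − 190/228 = 16.7% |
| 190 (design figure) | 0.900 | 0.868 | 0.826 | 0.774 | any loss |

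**4. False-positive rate if sites are chosen with results known.** The protocol plans 50-60 centres. Assumed: 228 patients over 55 sites of gamma-distributed size, blocks of 4 within site, median 13 days in both arms, censoring at 77 days. Sites are removed one at a time to maximise the log-rank Z, and error is P(Z > 1.96) in favour of the drug. Each scenario has 20,000 null replicates, with Monte Carlo error of at most ±0.7 percentage points.

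| Sites that could qualify | None dropped | Up to 1 | Up to 2 | Up to 3 | Up to 5 |
|---|---|---|---|---|---|
| 10 | 2.4% | 4.0% | 5.1% | 5.8% | 6.3% |
| 20 | 2.4% | 4.7% | 7.1% | 9.0% | 12.2% |
| All 55 (ceiling) | 2.5% | 6.1% | 11.2% | 17.5% | 33.6% |

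A simpler model (190 patients, score-test approximation, every unfavourable candidate site dropped) gives 3.5%, 4.3% and 7.1% for 3, 5 and 10 candidate sites, which is the same scale.

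**5. If sites are chosen blind.** Random removal of 1 to 5 whole sites (4,000 replicates) gives 2.8-2.9%, against 2.9% with none removed. The rate does not change.

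**The case against.** The bullet names no population. One of its neighbours, early termination, is a matter of trial conduct, so the heading does not settle its scope, and dropping patients could mean closing sites. SAP section 9 allows exceptions to the mITT, and the contrast between current practice and what will be done may signal an intended departure. Of this, it stands that the scope has to be inferred. The conduct reading is nevertheless weak: the words concern patients, the heading concerns analysis, and sensitivity analyses have their own item. A deliberate departure would still need a criterion and a revised population definition.

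The design also offers some protection. Randomisation is stratified by site, so removing whole sites blind largely preserves balance. The trial is double-blind, and routine DMC data are shown as groups A and B. Protocol Amendment 3 dates from September 2019 and could not have foreseen the pandemic. All of this is true, but the rule requires neither whole-site removal nor a blind choice, and the SAP, which does address the pandemic, could have required both.

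On size, the 33.6% lets every site qualify, although the rule covers only sites with COVID-19 problems. That is fair: it is a ceiling, and with 3 to 10 qualifying sites the rate is roughly 3% to 7%. The power figures are also conditional. The 260 is enrolment, not evaluable patients. The 190 row assumes 0.938 events per patient; if all 190 had events, power would be 91.7%, and 90.3% after a 5% loss.

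Sensitivity analyses are promised, but not results with and without the dropped patients.

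**Conclusion.** The concern holds and should be fixed before any database lock. The SAP states a rule that can change who is in the primary test. The rule has no measurable criterion, decision maker, deadline or blinding condition, and it is not reconciled with the mITT definition in either document. The documents permit selection driven by outcome; they do not show that it happened.

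The missing blinding condition matters most. Blind removal of whole sites leaves the false-positive rate unchanged and costs power only. Under the stated assumptions, choice with results known takes the one-sided rate from 2.5% to about 6% with 10 qualifying sites and up to 5 dropped, and to about 12% with 20. The actual power loss cannot be derived, because the number dropped is unknown. The blind-removal result covers whole sites only; it does not extend to dropping selected patients for poor compliance, which treatment could influence.

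**What to change.** - Delete the drop-patients item as a main-analysis rule. State that every patient who meets the Safety, ITT or mITT definition stays in the corresponding analyses, whatever the site.
- Make exclusion of affected sites, or of assessments after 1 January 2020, a sensitivity analysis only, reported beside the full-population result.
- Write objective criteria for an affected site into the SAP, for example the share of scheduled WHO assessments missed. Say that whole sites, not selected patients, are excluded in that analysis.
- Have blinded staff sign and date the site list before the first of the two database locks.

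The cost is SAP wording and one sensitivity table. The drawback is that noisier data from affected sites remain in the primary analysis.
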